In general, loss of 80% of beta cell function is needed to develop severe hyperglycemia. Endogenous insulin secretion is almost entirely lost within 3 to 5 years after the diagnosis ⁽⁵⁾. In children with new diagnosis of T1D, glucagon levels were highly associated with post prandial blood glucose, but not with HbA1c level ⁽⁶⁾. It has also been reported that postprandial hyperglucagonemia worsens significantly while C-peptide secretion declines during the first year of the disease ⁽⁷⁾. Also, in children with greater than five years of T1D, postprandial glucagon levels increased 160% from one to sixty months after diagnosis ⁽⁸⁾ and in those with disease duration of 6.9 + 4 years, glucagon levels were strongly correlated with post-prandial glucose and mildly correlated with HbA1C levels ⁽⁹⁾. A study in T1D adults performed in China showed that post-prandial glucagon levels were higher in T1D patients in the first year of the disease compared to those with longer course of the disease, and that hypoglycemic events were lower in newly diagnosed patients ⁽¹⁰⁾, suggesting that glucagon secretory function may become impaired with longer duration of the disease. These studies suggest that glucagon dysregulation could impact glucose control with exogenous insulin, and that this dysregulation may change with disease duration.

Insulin Timing and Hyperglycemia in T1D:

Post-prandial hyperglycemia adds to glucose variability, difficulty with insulin dosing and overall instability of glucose control. A recent analysis from the T1D Exchange study, that included 4768 participants younger than 26 years with a clinical diagnosis of T1D for at least 1 year showed that 21% of the participants reported administering insulin several minutes before, 44% immediately before, 10% during, and 24% after meal. Interestingly, participants who reported administering insulin during or after a meal were more likely to report missing ≥ 1 mealtime insulin dose per week compared with those who administered insulin before meals ⁽¹¹⁾. In addition, a sub-analysis showed that participants who dose mealtime insulin in the postprandial period have poorer glycemic control and greater frequency of severe hypoglycemia ⁽¹²⁾. However, despite these recent results, patients are often advised to give insulin after eating

because caloric intake is uncertain.

Glucagon Regulation:

Different models have been used to study glucagon regulation ^(13,14,15,16). Since both hyperglycemia and hypoglycemia stimulate alpha cells to produce glucagon, both the lack of intra-islet insulin and this U-shaped glucagon response contribute to glucose dysregulation in T1D ^(17,18). It has been reported that in T1D patients with a duration of the disease of 26.4±7.5 years, glucagon levels increased in response to the OGTT under euglycemic and hyperglycemic conditions ⁽¹⁹⁾, however the relative contribution of hyperglucagonemia to post-prandial glucose rise in the presence or absence of pre-prandial insulin has not been clearly elucidated. Whether appropriately timed exogenous insulin can modify the glucagon response to glucose fluctuations has not been studied.

Research Objective:

To characterize the glucagon response to meal-time hyperglycemia and to compare the difference in glucagon secretion when mealtime bolus insulin is given before the meal versus after the meal with the objective of understanding factors that contribute to the peak post-prandial blood glucose and AUC of blood glucose after a mixed meal in this target population.

Research Hypothesis:

1. Patients with higher glucagon responses to a mixed meal stimulus will have higher peak post-prandial glucoses and greater AUC of post-prandial glucose.
2. Bolus dose insulin given pre-meal (20 min before meal) will result in lower peak post-prandial glucose, lower AUC and lower post-prandial glucagon levels
3. Bolus dose insulin given post-meal (20 min after meal) will result in higher peak post-prandial glucoses, higher AUC of post-meal glucose and higher glucagon levels
4. There will be a correlation between peak post-prandial glucagon response and post-meal glucose AUC, 0 to 180 minutes

Potential Contribution:

Glucagon regulation and response in persons with T1D at the basal state and in response to various stimuli remains unclear. An important gap in our knowledge is whether the timing of prandial insulin doses affects the glucagon response to a hyperglycemic stimulus in patients with T1D who have undetectable C-peptide. Understanding the mechanisms behind the higher post-prandial peak in glucose with delayed insulin administration may help clinicians guide appropriate timing of insulin administration for T1D patients with long course of the disease

METHODS

Recruitment:

Subjects will be recruited from the investigators' private patient population. Screening will be done over the phone and with review of medical records.

Inclusion criteria:

- Persons of all races, ethnicity and genders will be included, Age ≥ 18
- Type 1 Diabetes for >5 years
- HbA1c $\leq 9.5\%$
- Using either MDI or insulin pumps
- Patients using CGM may continue the use during the study, however glucoses will be measured by laboratory methods.
- Hemoglobin: Female 10.8 -17.05 g/dL and Males 11.7-19.25 g/dl
- Hematocrit: Female 32.8-48.7% and Males 37-55.3%

Exclusion criteria:

- Type 2 diabetes, monogenic diabetes, pancreatic diseases
- eGFR <60 ml/min/1.73m².
- Use of daily steroids, any route, for any purpose
- Pregnancy, prisoners, other vulnerable populations or persons unable to understand the protocol and provide written informed consent

Data Collection:

See Appendix A

LOCATION OF STUDY VISITS

The study will be conducted in the Washington University-Diabetes Center, Center for Advanced Medicine 13B and/or the Intensive Research Unit, Center for Outpatient Health 5th floor.

PROCEDURES

Study Visits (Visits will take approximately 4 hours)

- Informed Consent may be performed on a visit prior to Visits A/B – subjects will be provided informed consent
- Visits A and B will be performed in random order, these visits will take place on 2 separate days within 1 week of the first visit
- Demographics, Obtain medical and medication history, including review of diabetes history, medications and allergies will be recorded at the first study visit. Insulin doses and effectiveness of current carbohydrate ratio will be evaluated and recorded. Mealtime insulin doses will be established at the first study visit.
- Baseline glucose should be 80 to 180 mg/dl. In case baseline glucose is not in the target range, the investigator will determine if the subject should return and the study visit rescheduled.
- Urine pregnancy test for women of childbearing potential
- Brief physical exam performed at first study visit
- Vital signs, height and weight performed at each visit
- Meal tolerance tests with timed samples collected as noted below performed at Visit A & B. Administration of liquid meal and Mealtime insulin to be given via injection by a study nurse to standardize the administration procedure.
- C-peptide may be checked with the fasting labs at the first study visit
- A sample for future research will be obtained, about 5ml (1tsp.)
- Whole blood will be collected in vacutainers via an indwelling peripheral venous catheter with nursing supervision from the diabetes center at Washington University. Maximum blood collection will be about 20ml (4 tsp).

Visit A

- Glucose levels done fasting, 30, 60, 120, and 180 minutes
- Glucagon levels done fasting, 30, 60, 120, and 180 minutes
- Usual insulin dose will be administered 20 minutes prior to a mixed meal challenge with Ensure Plus*

Visit B

- Glucose done fasting, 30, 60, 120, and 180 minutes
- Glucagon levels done fasting, 30, 60, 120, and 180 minutes
- Usual insulin dose will be administered 20 minutes after the mixed meal challenge with Ensure Plus*

*Ensure Plus (Abbott Nutrition) at 6cc/kg (max 360 cc), content per 100 ml: carbohydrate 21.5 grams, protein 5.5 grams, with nursing supervision.

PROTECTION OF CONFIDENTIALITY

Data Security

Study data may be stored in REDCAP or on WUSM protected servers as well as collective data which will be stored in a locked cabinet in a locked office. Study staff will be required to have their own logon/password to access electronic data and access to paper charts will be limited to authorized study staff.

Blood Samples may be processed and stored in the Diabetes Center or in the Center for Outpatient Health clinical research unit (CRU) in a locked room with access restricted to study staff or delivered directly to the Washington University Core lab and the investigators lab for handling and analysis. Blood samples will be coded before sending to the laboratory. The samples may include a subject identification number and date of birth.

Plasma and serum specimens will be stored in a Washington University School of Medicine research Laboratory for future studies of other metabolic parameters relating to pancreatic function and/or insulin signaling; 5 ml of plasma and serum will be collected at one of the visits.

ASSESSMENT OF RISKS AND BENEFITS

Potential risks include:

- Mild pain from IV catheter insertion
- Hypoglycemia after insulin administration. Patient will be monitored by a physician and a nurse during the whole visit.

Methods

Alpha cell function will be assessed by measuring fasting and post-prandial glucagon and calculation Area under the Curve ratio (AUC-Glucagon 0-180min/AUC-Glucose 0-180min). Some of the participants characteristics will include in the study are: Demographics, BMI, history of DKA, DKA at onset of diagnosis, diabetes comorbidities (Retinopathy, cardiovascular, nephropathy, neuropathy), concomitant autoimmune disease, type and dose of insulin,

Methods of Data Analysis

Data analysis will be performed using STATA 15.1 for Windows (StataCorp LP, College Station, Texas, United States). The sample size calculation assumes that the peak postprandial glucose will increase by 80 +/-20 mg/dl in the pre-meal insulin group and 140 +/-20 mg/dl in the post-meal group. So, the expected mean peak of postprandial glucose will be up to 220 mg/dL for Visit A and mean peak postprandial glucose will be up to 280 mg/dL for Visit B. The sample size will have 80% power to detect a difference between groups at $p < 0.05$. We have assumed correlation between visits A and B of 0.5. The sample size was corrected by an anticipated loss of follow up of 10% of the participants. The calculated sample size is 10 participants with full

data sets available for 8 participants. The study randomization is designed as follows: 5 participants will first attend Visit A, and then Visit B. The 5 remaining participants will first attend Visit B and then Visit A. AUC of post-prandial glucose and glucagon and maximum postprandial peak of glucose and glucagon will be analyzed by using paired T student. Relationships between variables were assessed by a Spearman's correlation test.

REFERENCES

1. Cryer PE. Minireview: Glucagon in the pathogenesis of hypoglycemia and hyperglycemia in diabetes. *Endocrinology*. 2012;153(3):1039-1048. doi:10.1210/en.2011-1499
4. Yosten GLC. Alpha cell dysfunction in type 1 diabetes. *Peptides*. 2018;100:54-60. doi:10.1016/j.peptides.2017.12.001

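### The correlations for hypotheses 1 and 4 make no stated correction for fasting glucose, so starting level can distort them, in a direction the documents do not fix

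*Combined protocol and SAP*

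**What the plan says.** Under Research Hypothesis, item 1 reads: "Patients with higher glucagon responses to a mixed meal stimulus will have higher peak post-prandial glucoses and greater AUC of post-prandial glucose". Item 4 reads: "There will be a correlation between peak post-prandial glucagon response and post-meal glucose AUC, 0 to 180 minutes".

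Methods of Data Analysis gives the variables and the tests: "AUC of post-prandial glucose and glucagon and maximum postprandial peak of glucose and glucagon will be analyzed by using paired T student", followed by "Relationships between variables were assessed by a Spearman's correlation test". The Methods paragraph on alpha cell function defines a ratio, "AUC-Glucagon 0-180min/AUC-Glucose 0-180min". None of these places says whether AUC or peak is total or fasting-subtracted, and none adjusts for fasting glucose. Absolute peak and total AUC are the plain reading, but those words are not in the plan.

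Two other places speak of a rise. The Glucagon Regulation background says that the "relative contribution of hyperglucagonemia to post-prandial glucose rise in the presence or absence of pre-prandial insulin has not been clearly elucidated". The sample size paragraph assumes peak increases of 80 and 140 mg/dL, each +/-20.

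On entry glucose, Study Visits says "Baseline glucose should be 80 to 180 mg/dl" and leaves out-of-range visits to the investigator. The Visit A and Visit B forms give 80 to 140 mg/dL with rescheduling. These passages contradict each other and must be reconciled.

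**The concern.** Absolute peak is starting glucose plus the rise. Total AUC 0-180 is 180 times starting glucose plus the area of the rise, so each mg/dL at entry adds 180 mg·min/dL. In the paired comparison of Visits A and B, stable differences between people in starting glucose cancel. In a Spearman correlation across people they do not: they help set the ranking.

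If much of the ranking reflects where glucose stood that morning, the coefficient does not isolate the link between glucagon and the meal rise. Depending on how fasting glucose relates to glucagon, a real link could be hidden or an apparent one could come from baseline alone. Leaving total versus incremental undefined also allows the choice to be made after the data are seen.

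**Working it through.** **The plan's own figures.** Expected peaks are up to 220 and 280 mg/dL. 220 − 80 = 140 and 280 − 140 = 140, so the plan itself builds peak as a start (up to 140) plus a rise. Its 10 participants, 8 with full data, were sized for the paired peak comparison. With SD 20 at each visit and correlation 0.5, the SD of the difference is √(400 + 400 − 2×0.5×400) = 20. For a difference of 60, a paired t-test has 74.5% power with 3 people and 96.7% with 4. Eight completers are reproduced only if pairing is ignored (4 per group, 93.9%). No calculation supports the correlations.

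**Inputs.** From the documents: entry windows of width 100 or 60 mg/dL; rise SD 20 (reading +/-20 as an SD); 8 completers. Assumed: uniform entry values, so SD = width/√12 = 28.9 or 17.3; start independent of rise; AUC of k = 80-137 minutes per mg/dL of peak rise, covering a range of curve shapes.

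**Share of between-person variance due to starting glucose.**

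- Peak: SDb² / (SDb² + 20²)
- Total AUC: (180·SDb)² / [(180·SDb)² + (20k)²]

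| Case | AUC, 80-180 | AUC, 80-140 | Peak, 80-180 | Peak, 80-140 |
|---|---|---|---|---|
| Uniform, rise SD 20, k = 80-137 | 78-91% | 56-79% | 68% | 43% |
| Window = 6 SD, rise SD 20, k = 80-137 | 55-78% | 30-56% | 41% | 20% |
| Uniform, rise SD 40, k = 114 | 56% | 32% | 34% | 16% |

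**Direction.** Let r be the correlation of glucagon with the rise and c its correlation with starting glucose. For peak, the correlation obtained is (c·SDb + 20r) / √(SDb² + 20²).

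- c = 0, r = 0.5: 10/35.1 = 0.28 (80-180); 10/26.5 = 0.38 (80-140).
- c = 0.3, r = 0.5: 0.53 and 0.57, so no attenuation. Break-even at r = 0.5 is c = 0.26 and 0.19.
- c = −0.3, r = 0.5: 0.04 and 0.18.

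**Simulated Spearman test.** 60,000 runs, n = 8, k = 114, uniform entry values, rise SD 20; two-sided significance at |rho| ≥ 0.738. Cells show mean rho; the share of runs significant is in brackets.

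| r with rise | c with start | Incremental AUC | Total AUC, 80-180 | Total AUC, 80-140 |
|---|---|---|---|---|
| 0.8 | 0 | 0.72 (59%) | 0.26 (9%) | 0.39 (16%) |
| 0.5 | +0.3 | 0.43 (19%) | 0.40 (17%) | 0.46 (21%) |
| 0 | +0.3 | 0.00 (5%) | 0.24 (8%) | 0.21 (7%) |
| 0.8 | −0.3 | 0.72 (59%) | 0.03 (4%) | 0.18 (6%) |

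For absolute peak with r = 0.8 and c = 0, 14% (80-180) and 27% (80-140) of runs are significant.

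**The case against.** The hypotheses name peak and AUC, not increments, and the Research Objective asks what contributes to those same quantities. Overall glucose exposure is a legitimate target, so preferring increments is partly a choice of estimand. This stands, and it is why the uncorrected correlations should still be reported.

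A reader might infer that the planned test always pulls a real link towards zero. The documents do not support that. It requires fasting glucose to be unrelated to glucagon, which is nowhere stated, and the background says that both high and low glucose stimulate glucagon release. With a link of +0.3 the attenuation is essentially gone at a true correlation of 0.5.

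A reader might also infer that the ranking is mostly starting glucose. With a rise SD of 20, that holds for total AUC in the 80-180 window under both spreads tried. It fails for peak in the 80-140 window, and for AUC in that window if entry values cluster or the rise SD is 40. The documents give no SD for entry glucose, and the 20 is a planning assumption.

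Finally, the correction does not rescue the test. With 8 people, incremental AUC has about 19% power at a true correlation of 0.5, 41% at 0.7 and 59% at 0.8. That stands too. What none of this answers is that the plan does not define its correlation variables or say how fasting glucose is handled.

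**Conclusion.** The point holds in a limited form. The plan would test hypotheses 1 and 4 on glucose variables with no stated fasting correction, although its background asks about the rise. Starting glucose can be a large part of the between-person ranking: more than half of total AUC variance in either window if entry values are uniform and the rise SD is 20, but as little as about 30% for AUC and 16% for peak under other plausible inputs. The resulting distortion has no fixed direction. It is attenuation if fasting glucose is unrelated to glucagon, and it can be inflation, or a correlation from baseline alone, if they are positively related. These sizes rest on the assumed entry distribution, curve shape, rise SD and independence of start and rise. A modest change to the analysis text is justified. It does not affect the paired comparison for which the trial was sized.

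**What to change.** In Methods of Data Analysis, state that for hypotheses 1 and 4, separately at each visit, the glucose variables are peak minus fasting and net incremental AUC (AUC 0-180 minus 180 × fasting). A partial Spearman correlation given fasting glucose is an acceptable alternative. Report the absolute-peak and total-AUC correlations alongside. Add that, with 8 completers, a null correlation will not be read as absence of a link. Separately, reconcile the two entry-glucose windows.

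The cost is a few sentences and no new samples, since fasting glucose is already drawn at both visits. There are two small downsides: measurement error in the single fasting value enters the increment, and the partial version loses one degree of freedom.

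### Known gastroparesis is not an exclusion, although Visit A gives every participant the usual bolus 20 minutes before the meal: a small, supervised but avoidable hypoglycaemia risk

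*Combined protocol and SAP*

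**What the plan says.** The Exclusion criteria have four items. The first is "Type 2 diabetes, monogenic diabetes, pancreatic diseases". The others are an eGFR below 60, daily steroid use, and a combined item on pregnancy, vulnerable groups and inability to consent. Gastroparesis and delayed gastric emptying appear nowhere in the supplied text, and there is no general exclusion at the investigator's discretion.

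The Inclusion criteria require "Type 1 Diabetes for >5 years" with no upper limit on duration. Under Recruitment, "Subjects will be recruited from the investigators' private patient population", and "Screening will be done over the phone and with review of medical records".

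At Visit A the usual dose goes in 20 minutes before the Ensure Plus meal; at Visit B, 20 minutes after it. A study nurse injects the dose at both. The section on risks and benefits names hypoglycaemia after insulin as a risk.

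**The concern.** Visit A fixes the interval between insulin and food for everyone. A person with delayed gastric emptying absorbs the meal later than the timing presumes, so insulin given first may lower glucose before carbohydrate arrives. This mechanism is general clinical reasoning and not a statement in the protocol.

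What is at stake is participant safety at the visit where insulin comes first. Read literally, the criteria let staff enrol someone whose record already shows gastroparesis and then apply the sequence least suited to that person. In a mechanistic study of 10 people, this risk can be reduced at almost no cost.

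**Working it through.** The plan states no figure on this point, so the check is a reading of its parts side by side.

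**Step 1. Could an existing criterion exclude a known case?** The four exclusion items concern diabetes type and pancreatic disease, renal function, steroids, and pregnancy, vulnerability or consent. None reaches gastroparesis. Neuropathy is recorded as a participant characteristic (Methods, and the data collection form) but has no role in eligibility.

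**Step 2. Does the protocol create the exposure?** Yes. The 20-minute lead at Visit A is assigned and does not depend on how the person normally doses. The background section reports that 24% of one surveyed cohort took mealtime insulin after eating. That cohort was younger than 26 years, so it is context only, but it shows that a usual dose need not have been worked out for pre-meal timing.

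**Step 3. What do the existing safeguards do?**

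| Safeguard | Where | Effect | What it leaves open |
|---|---|---|---|
| Investigators' own patients, record review | Recruitment | A known diagnosis is likely to be seen | No criterion says to act on it |
| History, carbohydrate ratio reviewed, dose established at first visit | Study Visits | Dose can be set individually | Timing at Visit A stays fixed |
| Baseline glucose of at least 80 mg/dl | Study Visits; data form | Avoids starting low | Checked before the meal, so it cannot show slow emptying |
| Liquid meal | Study Visits | Fixes the form of the meal | Nothing is said about emptying rate |
| Glucose at 30 and 60 minutes | Visit A, Visit B | Early readings after the start | No rescue or stopping threshold in the supplied text |
| Hypoglycaemia history and unawareness, gastrointestinal examination | Data form | Flags some vulnerable people | Recorded only, not tied to eligibility |
| Field for whether the intervention was held, with reason | Data form, both visits | Foresees withholding | No condition for holding is attached |
| Physician and nurse monitoring | Risks and benefits | Detection and response | Acts once glucose is falling, not at enrolment |

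The upper limit for baseline glucose is 180 mg/dl in the body and 140 mg/dl on the form. The floor is 80 mg/dl in both, and only the floor matters here.

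**Step 4. What remains?** Taken together, the safeguards make an unnoticed or untreated event unlikely. None says that a person with known gastroparesis should not be enrolled. The gap is therefore one of eligibility, and the residual risk is a supervised one.

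**The case against.** The strongest opposing case is that this is one reviewer's preferred criterion. The investigators recruit from their own practice and review records, so they are the people best placed to know who has gastroparesis and may simply not approach them. Doses are individual, the visit is supervised, and hypoglycaemia is already a named risk. Other conditions, such as hypoglycaemia unawareness, bear at least as directly on insulin-induced lows and are not excluded either.

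Much of this stands. It is why the risk is called small and the change optional. It does not remove the point: relying on unwritten judgement is weaker than one written line, and gastroparesis bears specifically on the insulin-to-meal interval that Visit A imposes.

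A reader might also infer a threat to the glucagon result. The protocol notes "Since both hyperglycemia and hypoglycemia stimulate alpha cells to produce glucagon", so a low glucose at Visit A could raise glucagon where Hypothesis 2 expects early insulin "will result in lower peak post-prandial glucose, lower AUC and lower post-prandial glucagon levels". Such a response would also lie outside the stated aim, "To characterize the glucagon response to meal-time hyperglycemia". Pairing and random order would not cancel it, because it would act on the within-person difference. But the documents do not show that it would matter. It would run against the hypothesis and so would not manufacture support for it. It may be weak in this population, since the background cites a study "suggesting that glucagon secretory function may become impaired with longer duration of the disease". The plan also gives no SD or effect size for glucagon from which to compute a loss.

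**Conclusion.** The point holds as a minor safety improvement. The omission is certain from the text. The harm rests on general clinical reasoning about delayed emptying, and on the assumption that a known case could otherwise be enrolled.

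The size of the risk cannot be set. The documents give no prevalence of gastroparesis, and participants are chosen from patients the investigators know. Assuming a prevalence and computing the chance of an affected participant among 10 would only return the assumption.

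Two further readings are tempting and unsupported:

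- A reader might infer that the peak-glucose comparison is at risk. An early low does not imply that insulin timing has no effect on that person's peak, and nothing in the documents links the two.
- A reader might treat the carbohydrate load of the meal as the hazard. The meal is the counterweight to the insulin; the hazard is insulin acting before the carbohydrate is absorbed.

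No effect on the peak-glucose or glucagon conclusions is shown.

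**What to change.** Add one line to the Exclusion criteria: *Known gastroparesis*, checked in the medical-record review already planned at screening.

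This needs no extra visit, blood draw, test or staff, and it leaves the sample-size figures unchanged. The costs are a slightly narrower population, so that the result applies less directly to all patients with long-standing type 1 diabetes, and an incomplete remedy, because undiagnosed delayed emptying will not be caught. The existing monitoring should therefore stay as it is.

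### Visit order is randomised but left out of the paired t-test; adding a period term is a cheap gain in precision, chiefly for AUC and glucagon

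*Combined protocol and SAP*

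**What the plan says.** Under Procedures, Study Visits: "Visits A and B will be performed in random order". Methods of Data Analysis fixes the split: "5 participants will first attend Visit A, and then Visit B", and the remaining five attend in the reverse order. For the analysis, the same section says that the AUCs and the "maximum postprandial peak of glucose and glucagon will be analyzed by using paired T student". The only other method named is Spearman's correlation. Visit order, period and sequence appear nowhere in the analysis.

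That section also gives the planning figures. Peak glucose rises as follows: "the peak postprandial glucose will increase by 80 +/-20 mg/dl in the pre-meal insulin group" and "140 +/-20 mg/dl in the post-meal group". On correlation: "We have assumed correlation between visits A and B of 0.5". On loss, it allows for an "anticipated loss of follow up of 10% of the participants" and expects full "data sets available for 8 participants".

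**The concern.** In a crossover, a systematic difference between first and second visits enters the post-meal-minus-pre-meal differences with one sign in one sequence and the opposite sign in the other. A plain paired t-test treats that spread as random error. The interval widens, and if the sequences lose different numbers of people the two signs no longer cancel in the mean.

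Order is randomised and known for every participant, so this error can be removed without new data. It matters most where the plan has least margin: the AUC and glucagon outcomes have no stated effect size, SD or power, and only 8 to 10 people contribute. A conceivable source of a visit difference is that history-taking, review of the carbohydrate ratio, dose-setting and physical examination are assigned to the first visit. That does not show that a period effect exists, only that it cannot be excluded beforehand.

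**Working it through.** **Inputs (Methods of Data Analysis).** Rise in peak glucose 80 and 140 mg/dL, a contrast of 60; spread 20 at each visit, read here as an SD because the plan does not label it; correlation 0.5; 10 enrolled, 5 per sequence; 8 full data sets, or 9 at 10% loss. The period effect π (second visit minus first, mg/dL) is not in the documents and is varied.

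**Planning figure.** SD of the within-person difference = √(20² + 20² − 2 × 0.5 × 20 × 20) = 20 mg/dL. On these inputs a two-sided paired t-test needs only 4 completers for 80% power (74.5% at 3, 96.7% at 4), and 8 give more than 99.9%. The stated 8 and 10 therefore do not follow from the paired inputs. That is a separate matter, but it shows that the peak-glucose contrast has a wide margin.

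**Model.** Let τ be the timing effect (B minus A) and d = B − A.
- A then B: mean of d = τ + π. B then A: mean of d = τ − π.
- Paired mean: bias = π(nAB − nBA)/n. This is 0 at 5:5 or 4:4, π/9 at 5:4 and π/4 at 5:3.
- Expected variance of d in the paired test: 20² + 4π²·nAB·nBA/[n(n − 1)].
- Adjusted estimate: average of the two sequence means of d, with SE = ½·s·√(1/nAB + 1/nBA), where s is the SD pooled within sequences, on n − 2 df. π cancels.

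**Hand check, 4:4, π = 20.** Paired: 2.365 × √(400 + 457.1)/√8 = 24.5. Adjusted: 2.447 × 20 × ½ × √(1/4 + 1/4) = 17.3. These use the root of the expected variance. The average half-width in repeated samples is slightly smaller and is used below.

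**Simulation** (normal data; 200,000 runs per setting, 100,000 for 5:5). Mean 95% half-width in mg/dL, paired v adjusted:

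| Completers | π = 0 | π = 5 | π = 10 | π = 20 | Paired bias at π = 5, 10, 20 |
|---|---|---|---|---|---|
| 5:5 | 13.9 v 14.1 | 14.4 v 14.1 | 15.8 v 14.1 | 20.4 v 14.1 | 0, 0, 0 |
| 4:4 | 16.1 v 16.6 | 16.7 v 16.6 | 18.3 v 16.6 | 23.8 v 16.6 | 0, 0, 0 |
| 5:3 | 16.1 v 17.1 | 16.7 v 17.1 | 18.2 v 17.1 | 23.4 v 17.1 | 1.25, 2.5, 5 |

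At 5:4 with π = 20 the half-widths are 21.8 v 15.3 and the paired bias is 2.2.

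- **Error rate.** Paired type I error at π = 10 and 20 is 3.1% and 0.7% at 4:4, and 4.0% and 2.0% at 5:3.
- **Break-even.** Adjustment gives the narrower interval above π of about 4.5 mg/dL (0.22 SD of the difference) at 4:4 and 6.9 mg/dL (0.34 SD) at 5:3. Below that the paired test is slightly better.
- **Power, 60 mg/dL.** Above 99.9% with the paired test for π up to 20 in every split examined; 90% in an extreme case (π = 40, 3:5).
- **Power, an assumed effect of 1 SD, 4:4, paired v adjusted.** 68% v 66% with no period effect, 58% v 66% at π = 0.5 SD, 34% v 66% at π = 1 SD.
- **Chance of imbalance.** If two of ten are lost at random, 4:4 has probability (5 × 5)/45 = 56% and 5:3 or 3:5 has 44%.

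**The case against.** The planned test is not invalid. Its type I error does not rise, its coverage is at or above nominal, and the one powered contrast is secure. With balanced completers the two methods give the same point estimate. The gain depends on a period effect that the documents do not quantify, and several features may keep it small: random order, a one-week window, the same meal, a nurse-given injection and a baseline glucose window. Under random loss the expected bias is zero. At 5:4 a period effect of 10 shifts the estimate by only 10/9 = 1.1 mg/dL. The 34% v 66% case assumes a period effect as large as the timing effect. The adjusted model also assumes no differential carry-over, and the mg/dL figures rest on reading the stated spread as an SD and applying it to the peak, although the plan gives it for the rise.

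All of this stands, and it limits the weight of the point. It does not remove it. The variance penalty exists even at 4:4, and a single trial has to report at the split it ends up with. Differential carry-over would bias the paired test too. A different SD rescales the mg/dL thresholds (an SD of 40 would double 4.5 to about 9) but leaves the SD-scaled ones unchanged.

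**Conclusion.** The point holds as an inexpensive improvement, not as a flaw that invalidates the analysis. The trade is uneven. With no period effect, adjustment widens the interval by about 3% at 4:4 (16.6/16.1) and 6% at 5:3 (17.1/16.1). With a period effect of 20 mg/dL, leaving order out makes the 4:4 interval about 43% wider than the adjusted one (23.8/16.6). At 5:3 it makes the interval about 37% wider (23.4/17.1) and shifts the estimate by 5 mg/dL. The conclusion on the planned 60 mg/dL contrast would hardly change; the benefit is for smaller effects and for AUC and glucagon. The figures assume normal differences with SD 20 mg/dL, no differential carry-over, and period effects chosen for illustration.

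**What to change.** Specify in the SAP, before data are seen, that the main analysis of each endpoint is a linear model with participant, period and insulin timing. The equivalent is a two-sample t-test comparing second-minus-first-visit differences between the two sequences, with the contrast halved to give the timing effect. Post-meal-minus-pre-meal differences must not be compared between sequences, because that tests the period effect. Report the timing effect with its 95% CI and the number of completers in each sequence, state the no-carry-over assumption, and keep the plain paired t-test as a sensitivity analysis.

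This changes SAP wording only and needs no extra data or visits. The price is one degree of freedom.
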